In this pilot study, 24 participants will be accepted from our referral sources in the department of Neurology and Physical Medicine. There will be 2 measurement periods before the training starts, separated by 3-14 days in order to establish baseline word-finding performance on selected trained and untrained word lists. Following the lead-in period, subjects will participate in a cross-over design training period to compare the two tDCS conditions (1mA anodal vs. sham). The training portion of the study will occur over a total of 3 weeks. During that time, subjects will attend five consecutive, 60-minute training sessions under treatment condition one (anodal vs. sham tDCS), followed by a 1 week rest interval, and then another five consecutive sessions of training under treatment condition two. Order of training word lists and tDCS stimulation condition will be counterbalance across participants. Subjects will undergo four additional evaluations throughout the course of the study, two of which will occur immediately after each of the training conditions (discharge), and the other two of which will occur 1 week after each training condition (follow-up). All study procedures will be administered or supervised by the research coordinator or another licensed Speech-Language Pathologist. All visits will be conducted in the clinical robotics and non-invasive brain stimulation suite at the Feinstein.

Lead-in Period

- Week 1, Visit 1 (approximately 60 minutes)
 - Baseline outcome measures
 - Medical screening
 - Consent
- Week 2, Visit 2 (approximately 60 minutes each)
 - Baseline outcome measures

Training Period Phase I

- Week 3, Visit 3-6 (approximately 60 minutes)
 - 20 min of stimulation condition 1 (sham or anodal tDCS) and 20 min of computerized word-picture matching therapy
- Week 3, Visit 7 (approximately 90 minutes)
 - 20 min of stimulation condition 1 (sham or anodal tDCS) and 20 min of computerized word-picture matching therapy
 - Condition 1 discharge outcome measures

Follow Up Testing Phase I

- Week 4, Visit 8 (approximately 60 minutes)
 - Condition 1 follow-up outcome measures

Training Period Phase II

- Week 5, Visit 9-12 (approximately 60 minutes)
 - 20 min of stimulation condition 2 (sham or anodal tDCS) and 20 min of computerized word-picture matching therapy
- Week 5, Visit 13 (approximately 90 minutes)
 - 20 min of stimulation condition 2 (sham or anodal tDCS) and 20 min of computerized word-picture matching therapy

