This self-administered computerized anomia treatment was reported on in a previous study, and demonstrated to be helpful in improving naming accuracy of individuals with aphasia (4). Subjects are asked to perform a 20-minute picture-word matching task following receipt of either sham or anodal tDCS.

Randomization

A single-subject cross-over design will be used to compare two tDCS conditions (1mA anodal vs. sham). The order of anodal or sham stimulation will be counterbalanced across participants, and determined using a random number generator.

Blinding

This is a double blind study. The tDCS device will be covered such that the administrator will code each stimulation condition as either switch “up” or switch “down,” but will remain blinded to which code is anodal vs. sham stimulation. In this way, all investigators interacting with patients will remain unaware of stimulation condition. For the sham condition, the stimulation automatically ramps down after 30 seconds because the perceived sensation of tDCS on the skin has been reported to fade after this period (21). Consequently, participants will also stay blinded to stimulation condition.

Statistical Considerations and Data Analysis

SPECIFIC AIM 1: To evaluate whether anodal tDCS preceding aphasia therapy significantly improves picture naming in individuals with post-stroke aphasia.

Methods to address specific aim 1: A Wilcoxon signed-rank test will be used to compare naming accuracy scores pre and post anodal tDCS condition across participants.

SPECIFIC AIM 2: To compare naming performance between intervention conditions (tDCS and sham stimulation).

Methods to address specific aim 2: If neuromodulation preceding treatment is effective for promoting recovery in language impairment, as it is in robotic hemiplegia treatment, we expect the improvement in naming accuracy to be greater following anodal tDCS compared with sham tDCS. This will be examined with a 2x2 repeated measures ANOVA for both treated and untreated items with stimulation type (A-tDCS,S-tDCS) and time (T1, T2) as factors.

SPECIFIC AIM 3: To compare naming performance between severity groups (high vs. low functioning aphasia as determined by admission Western Aphasia Battery scores (WAB)).

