numerous studies applying tDCS with human participants (22-24). tDCS has the potential to cause erythema – redness of the skin that is uniform or mottled around the area of stimulation. The reddening has been found to be transient for level of stimulation proposed in this protocol (20-21).

Confidentiality Risk: One additional risk concerns the risk to confidentiality incurred with any collection of medical data.

ADEQUACY OF PROTECTION AGAINST RISKS

Recruitment and Informed Consent: Stroke subjects who meet inclusion criteria and do not meet exclusion criteria will be recruited by consenting professionals through the Department of Physical Medicine and Rehabilitation of NSUH and LIJMC. Recruitment will be done with direct contact and flyers.

Northwell Health Health physicians and clinicians who have appropriate patient populations will be made aware of the research study protocol and procedures, and given an overview of the study through contacts with the study personnel. These clinicians will identify potential study participants. If the patient expresses interest in participation, the clinician will either: 1.) provide the patient with the study coordinator's contact information or 2.) provide the patient's contact information to study personnel.

Investigators may contact (or be contacted by) a potential subject or subject's LAR/next-of-kin by telephone to discuss participation in this research protocol. The investigator will provide the subject/LAR/next-of-kin with all the information contained in the written consent form. The investigator will answer any questions regarding the research and give the subject/LAR/next-of-kin ample time to consider participation in the study which may require a follow-up phone conversation.

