Protection Against Risk:

Protection against tDCS-related risks: If any redness is apparent where the electrodes were placed, a cold compress will be offered to the subject. We will monitor subjects continually during the stimulation period, and will be in constant contact with the subjects. The study can be immediately stopped at the subject's request.

Protection of Confidentiality: To protect subjects' confidentiality, each subject will be assigned an ID number, and all data will be stored with the subject ID number only and not the subject's name. Data will be stored on a password-protected computer and on Feinstein's data server, REDCap. The *Feinstein Institute for Medical Research* will be used as a central location for data processing and management. Vanderbilt University, with collaboration from a consortium of institutional partners, has developed a software toolset and workflow methodology for electronic collection and management of research and clinical trial data. REDCap (Research Electronic Data Capture) data collection projects rely on a thorough study-specific data dictionary defined in an iterative self-documenting process by all members of the research team with planning assistance from the Biostatistics Unit of the *Feinstein Institute for Medical Research*. The iterative development and testing process results in a well-planned data collection strategy for individual studies. REDCap servers are housed in a local data center at the Feinstein and all web-based information transmission is encrypted. REDCap was developed specifically around HIPAA-Security guidelines and is recommended to Northwell Health researchers by both our Clinical Research Service, Research Compliance Office and Institutional Review Board. REDCap has been disseminated for use locally at other institutions and currently supports 965 active institutional partners and other institutions in 78 countries (www.project-redcap.org) Subject charts with medical history and assigned subject numbers will be kept in locked file cabinets stored at the Feinstein robot suite. Access to charts will be granted only to study investigators. Charts will be kept confidential and will not be shared with any third parties without permission from the subject. Any study data containing PHI that is transferred between investigators at Feinstein and collaborating institutes will be shared via encrypted email or encrypted storage drives.

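### The Blinding section describes a two-position switch code with no participant-specific coding, so any anodal–sham difference in skin redness would accumulate across participants towards one answer for the whole trial

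*Combined protocol and SAP*

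**What the plan says.** The protocol calls the study double blind. Under the Blinding section the stimulator is hidden from view, and the two conditions are told apart only by an up or down setting. The person operating it knows that setting, "but will remain blinded to which code is anodal vs. sham stimulation". From this the section concludes: "In this way, all investigators interacting with patients will remain unaware of stimulation condition". It does not mention a separate code per participant, re-coding between participants, who holds the key, or any check of the blind. Participant blinding is argued from the fading of skin sensation; redness is not discussed there.

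Other sections bear on the point:

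- **Crossover (Randomization):** "The order of anodal or sham stimulation will be counterbalanced across participants, and determined using a random number generator".
- **Sessions (Visit Schedule):** "subjects will attend five consecutive, 60-minute training sessions under treatment condition one (anodal vs. sham tDCS), followed by a 1 week rest interval", then five more under the other condition. Both switch positions are therefore used in every participant who completes the study. Discharge measures are taken at Visits 7 and 13, which are also stimulation visits.
- **Staff (Visit Schedule):** "All study procedures will be administered or supervised by the research coordinator or another licensed Speech-Language Pathologist".
- **Exposure (tDCS Application):** anodal current is 1 mA for 20 minutes. Sham is a 30-second ramp to 1 mA, 5 seconds, then a slow decrease of unstated length.
- **Redness (Potential Risks):** "tDCS has the potential to cause erythema", described as transient, with no rate for either condition.
- **Response to redness (Protection Against Risk):** "If any redness is apparent where the electrodes were placed, a cold compress will be offered to the subject".
- **Scoring (Naming Probes):** responses are recorded and scored later by an SLP. The section does not say whether that person is separate from treating staff or masked to switch code and period.

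**The concern.** With a two-position code of fixed meaning, the whole allocation of the trial hangs on one binary unknown. A crossover supplies a comparison of the two positions within each person, and every further participant adds to the same tally. Staff who must stay blind are also the ones who see and respond to redness at the electrode site, a cue that the protocol itself names and that the different exposure times could make more frequent under anodal current.

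Under a fixed code, a correct guess is not confined to one participant. It reveals every period already completed and every period still to come, including discharge testing done at the same visit as stimulation. Aim 2 is the main sham-controlled comparison, and Aim 3 uses the same anodal and sham changes. The protocol states in advance which direction it expects for Aim 2. If the people who elicit or score naming responses know the condition, expectation can enter that contrast.

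**Working it through.** The plan states no figure for the security of the blind, so there is nothing to reproduce. The calculation below illustrates how a fixed code and a per-participant code differ.

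**Inputs from the documents.** Two switch positions; both conditions given to each participant; 24 participants according to the Visit Schedule and 12 according to Protection of Human Subjects, so both numbers are shown.

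**Assumed inputs.** The probability that redness is noticed at least once in a participant's five-session block: a for anodal, s for sham. Each participant counts once per condition. Blocks are independent. The observer remembers all cases and pools them by switch position. These rates are not in the documents, so a range that includes equal and low rates is used.

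**Fixed code.** After n participants, let A ~ Binomial(n, a) be the number with redness under the anodal position and S ~ Binomial(n, s) the number under the sham position. The observer names the position with more redness as anodal and tosses a coin on a tie:

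P(correct) = P(A > S) + ½ P(A = S)

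**Per-participant code.** One participant's redness says nothing about another's code, so n = 1 applies throughout. The formula reduces to

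P(correct) = a(1 − s) + ½[as + (1 − a)(1 − s)] = ½ + (a − s)/2

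For 40% vs 20%: 0.50 + 0.20/2 = 0.60. For 20% vs 10%: 0.50 + 0.10/2 = 0.55. For 10% vs 5%: 0.50 + 0.05/2 = 0.525.

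**Worked case, fixed code, 20% vs 10%.** At n = 12, P(A > S) = 0.657 and P(A = S) = 0.185, so P(correct) = 0.657 + 0.093 = 0.75. At n = 24 the two terms are 0.783 and 0.102, giving 0.783 + 0.051 = 0.83.

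| Assumed redness, anodal / sham | Per-participant code | Fixed, n = 6 | Fixed, n = 12 | Fixed, n = 24 |
|---|---|---|---|---|
| equal | 0.50 | 0.50 | 0.50 | 0.50 |
| 10% / 5% | 0.525 | 0.61 | 0.67 | 0.74 |
| 20% / 10% | 0.55 | 0.68 | 0.75 | 0.83 |
| 40% / 20% | 0.60 | 0.77 | 0.86 | 0.94 |

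Under a fixed code the chance of a correct guess rises with every participant whenever the rates differ. Under a per-participant code it does not rise at all.

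**The case against.** Several objections have force.

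- **The fixed code is not stated.** The Blinding section never says that the mapping is the same for everyone. It speaks of one unknown and describes no re-coding, so a fixed mapping is the natural reading. If codes do vary, one added sentence settles the point.
- **That the same staff see both conditions is not stated.** The wording in the Visit Schedule allows more than one operator. Overlap is likely, but it is an inference.
- **Redness is informative only if the rates differ.** No rates are given, both conditions share a comparable set-up, and the reddening is called transient. The protocol does not tell staff to search for redness. It tells them to respond when it is apparent, and the continual monitoring it describes takes place during stimulation, when the electrodes cover the skin. The difference in exposure makes a difference in redness plausible and no more.
- **Safeguards limit the route to bias.** The therapy is a self-administered computer task, the probes are pictures on a laptop, the first complete response counts, and scoring is from recordings. This stands, and it narrows the exposed steps to live elicitation of the probes and to scoring, where masking is left open.
- **A per-participant code does not remove guessing.** It leaves the chance at up to 0.60 within a participant in the cases shown. What it stops is accumulation across participants.

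A reader might infer that a single red patch would break the blind for the whole trial at once, or that staff are certain to learn the code. The documents do not support this. One event would be decisive only if sham never caused redness, which is nowhere stated. At unequal but overlapping rates the blind erodes gradually, and at equal rates it does not erode through this cue.

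**Conclusion.** The point holds as a conditional weakness of the design that should be corrected. If the mapping is fixed and redness is commoner under anodal current, the protocol's claim that investigators stay unaware becomes less secure with each participant. After 12 participants the chance of a correct guess is 0.67 to 0.86 for the unequal rates shown, and after 24 it is 0.74 to 0.94, against 0.525 to 0.60 with participant-specific coding. With equal rates it is 0.50 under either scheme.

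These figures are illustrations. They rest on assumed redness rates, independent blocks, and an observer who pools every case; a less attentive observer, or several who do not share what they see, would do worse. The effect on the Aim 2 result cannot be sized from the documents. It depends on who administers and scores the probes and on what those people know.

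**What to change.** In the Blinding section:

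1. Have the random number generator that sets stimulation order also set, for each participant, which switch position is anodal.
2. Assign a named role with no patient contact to hold the mapping and set the covered device before each participant starts. The protocol identifies no key holder at present, so this role has to be created.
3. State that the SLP who scores the recordings works without access to switch code or period.

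Optionally, record guesses of the condition after outcome testing at Visit 13, so that the question does not prompt expectations before that testing, and report them beside the Aim 2 result. Follow-up testing at Visit 14 still comes later; waiting until it is done would protect it too. The guesses describe the state of the blind and do not repair it.

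The cost is a few sentences of protocol text, one more column in the randomisation list, resetting the device once per participant, and recordings labelled so as not to reveal code or period. The downside is a slightly higher chance of a set-up error. The sponsor should confirm that the covered device can be re-mapped, because the documents do not say. Sample size, visits, stimulation and planned tests are unchanged.

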Protocol Title: Evaluating Anodal tDCS Preceding Aphasia Therapy

Principal Investigator: [name].

Introduction

Aphasia is a communication deficit resulting from a brain injury or a stroke. It can affect one's ability to speak, understand, read, and write, though the hallmark symptom is a word-finding deficit. It is estimated that there are 80,000 new cases of aphasia per year in the United States, and approximately 1 million people in the United States today, suffer from aphasia (1).

Traditional aphasia therapy focuses on both training of compensatory strategies for communication and mass practice of communication skills with hierarchical cueing from an SLP (Speech and Language Pathologist). For example, an individual with aphasia may learn to point to pictures on a communication board to express wants/needs or practice simple object naming with progressively fewer and less supportive verbal or gestural cues. These therapy techniques have remained relatively unchanged since the early 1990's. Recent stroke rehabilitation research has suggested that non-invasive brain stimulation techniques, such as transcranial direct current stimulation (tDCS), may augment the benefits of traditional rehabilitation by modulating cortical activation, and priming the cortex for improved motor and cognitive recovery. tDCS combined with aphasia therapy has been shown to improve naming, verbal fluency, repetition, and linguistic cohesion for conversational narratives (2-10).

However, debate remains over the optimal parameters for cortical stimulation including intensity, location, polarity (anodal/cathodal), and timing. Most research on tDCS and language therapy has applied neurostimulation during language treatment (2, 4, 5, 8, & 10). However, others, using tDCS in patients recovering motor function after a stroke, have found the greatest improvement when anodal tDCS preceded robotic hemiplegia training (11). In a pilot study, we want to test the hypothesis that anodal tDCS delivered before language treatment will affect the naming ability in patients with aphasia after chronic stroke (greater than 6 months from acute injury).

Specific Aims

SPECIFIC AIM 1: To evaluate whether anodal tDCS preceding aphasia therapy significantly improves picture naming in individuals with post-stroke aphasia.

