In patients with chronic post-stroke aphasia, we will use a within-subjects repeated-measures design, to evaluate the effects of computerized mass practice audiovisual word-picture matching therapy (5 day/week x1 week) preceded by 20 min of anodal tDCS. Functional improvement will be determined by changes in naming accuracy on trained and untrained word lists.

We are aware that naming is one aspect of the language impairment that may occur after stroke. Thus, we will also measure other aspects of language function, so that if naming does not change there will be additional tests of the hypothesis.

SPECIFIC AIM 2: To compare naming performance between intervention groups (tDCS and sham stimulation).

We will use a single-subject cross-over design to compare two tDCS conditions (1mA anodal vs. sham). Treatment sessions will occur for five consecutive days per condition, with one week between conditions (3 weeks total). Functional improvement will be determined by changes in naming accuracy on trained and untrained word lists.

If neuromodulation (tDCS) preceding treatment is effective for promoting robust recovery in naming ability, as it has demonstrated for motor recovery in patients with chronic stroke and hemiplegia, then we expect the improvement in naming accuracy to be greater following anodal tDCS compared with sham tDCS.

These pilot results will support or not the continued investigation of novel non-invasive neuromodulation techniques.

SPECIFIC AIM 3: To compare naming performance between severity groups (high vs. low functioning aphasia as determined by admission Western Aphasia Battery scores (WAB)).

Preliminary Data

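### Aim 1 asks whether anodal tDCS improves naming, but its only test is a before/after comparison of therapy plus tDCS, and nothing stops a significant result being reported as a tDCS effect

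*Combined protocol and SAP*

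**What the plan says.** The Aim 1 heading appears under Specific Aims and again under Statistical Considerations and Data Analysis: "To evaluate whether anodal tDCS preceding aphasia therapy significantly improves picture naming in individuals with post-stroke aphasia". The single method given for it is "A Wilcoxon signed-rank test will be used to compare naming accuracy scores pre and post anodal tDCS condition across participants". Sham does not enter this test.

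The text below the Aim 1 heading in Specific Aims describes something different, a package: the study will "evaluate the effects of computerized mass practice audiovisual word-picture matching therapy (5 day/week x1 week) preceded by 20 min of anodal tDCS". The next paragraph there says other language measures are taken so that the hypothesis can still be tested if naming does not move. The hypothesis stated in the Introduction is about anodal tDCS.

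Aim 2 holds the controlled comparison. If neuromodulation works, "we expect the improvement in naming accuracy to be greater following anodal tDCS compared with sham tDCS", and this is examined with a "2x2 repeated measures ANOVA for both treated and untreated items with stimulation type (A-tDCS,S-tDCS) and time (T1, T2) as factors". The sentence on whether to continue this line of research also sits under Aim 2: "These pilot results will support or not the continued investigation of novel non-invasive neuromodulation techniques".

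Two further facts bear on the point. The Computerized Anomia Treatment section says the same 20-minute task follows both sham and anodal stimulation, and cites an earlier study in which that treatment helped naming accuracy. The Visit Schedule provides a double baseline: "There will be 2 measurement periods before the training starts, separated by 3-14 days".

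**The concern.** The question in the Aim 1 heading is about tDCS, but the test under it has no comparator for tDCS. On the protocol's own account, naming should rise in the anodal condition even if the stimulation is inert, because the therapy is expected to work. A significant Wilcoxon result would then answer the heading with a yes.

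Suppose the package shows a gain and there is no difference from sham. That pattern is coherent: it points to therapy or retesting, with no demonstrated contribution from tDCS. The plan does not rank the aims, does not call Aim 1 descriptive, and does not say which aim governs a statement about tDCS. The heading as worded would let that pattern be reported as tDCS significantly improving naming.

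**Working it through.** **What each test estimates.** Write the mean before/after change as a sum of parts: T for therapy, R for retesting, S for what anodal tDCS adds.

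- Anodal condition: T + R + S
- Sham condition: T + R
- Anodal minus sham: S (taking the shared parts as equal in the two conditions, with no period or carry-over effect)

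The Aim 1 test asks whether T + R + S is zero. The Aim 2 interaction asks whether S is zero. The two baselines precede any training, so they can inform on R but not on T. They do not rescue Aim 1 as a test of S.

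**Inputs.** From the documents: 24 participants (Visit Schedule) or 12 (Protection of Human Subjects), the Wilcoxon test and the 2x2 ANOVA. The documents give no power, significance level, effect size or SD, so there is no stated figure to reproduce. Assumed: S = 0; T + R = d, in SD units of the paired change; normally distributed changes; correlation 0 or 0.5 between conditions; two-sided 5%.

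**Method.** 200,000 simulated trials per setting.

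- Aim 1: exact signed-rank test. The critical value is 81 at n = 24 (true size 0.0491) and 13 at n = 12 (true size 0.0425).
- Aim 2: paired t test on anodal change minus sham change. Its square equals the interaction F of the 2x2 repeated measures ANOVA.

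**Results with no tDCS effect.** Where a range is shown, it covers correlations 0 and 0.5.

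| Assumed gain d | Aim 1 significant, n = 24 | Aim 1 significant, n = 12 | Aim 1 significant and Aim 2 not, n = 24 | Same, n = 12 |
|---|---|---|---|---|
| 0.25 | 21% | 11% | 19% | 9–10% |
| 0.5 | 63% | 31% | 60% | 29% |
| 0.8 | 96% | 67% | 91% | 63–64% |
| 1.0 | 99.5% | 85% | 95% | 81% |

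At d = 0 the Aim 1 test rejects in 4.8% (n = 24) and 4.2% (n = 12) of trials, as it should. The Aim 2 interaction rejects in 4.9% to 5.1% in every simulated setting.

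**How large a gain is needed.** Aim 1 is significant in half of trials at d = 0.43 (n = 24) or 0.66 (n = 12), and in 80% at d = 0.61 or 0.93.

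**Cross-checks.**

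- A separate simulation of 20,000 trials per setting gave 63.1% and 31.4% at d = 0.5.
- In that run the same before/after test in the sham condition gave 63.3% and 31.9%. The test behaves alike with and without active stimulation.
- The normal approximation Φ(d√n − 1.96) gives Φ(2.449 − 1.960) = 0.688 at n = 24 and Φ(1.732 − 1.960) = 0.410 at n = 12. It is somewhat optimistic at these sample sizes but shows the same pattern.

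**The case against.** The strongest reply is that the plan already handles this in substance. The trial is randomised in order, double-blind and sham-controlled. Aim 2 ties tDCS effectiveness to a larger gain with anodal than with sham, and the continuation sentence sits there too. The heading can be read as a sequence, tDCS and then therapy, which is how the text under it describes the design; for that question the Wilcoxon test is valid. On this view Aim 1 is within-condition change, Aim 2 is attribution, and any harm needs an author to ignore Aim 2. The simulated rates are also partly built in: adding a therapy gain must make a before/after test reject more often, every d is assumed, and the 5% for Aim 2 depends on equal gains in both conditions with no period or carry-over effect.

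Much of this stands. No test or data item is missing, and the percentages are power for the package. They become false attributions only if the result is read as a tDCS effect. What does not stand is that the text settles the reading. The heading makes tDCS the thing that improves naming, and the paragraph on additional measures treats naming change under Aim 1 as a test of the hypothesis, which the Introduction states as a tDCS hypothesis. No sentence limits Aim 1 to the package.

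**Conclusion.** The concern holds. The question in the Aim 1 heading cannot be answered by its only test, and the heading conflicts with the package described beneath it. The trial does contain a valid tDCS comparison, so the fault lies in what Aim 1 is allowed to conclude, not in the design. It should be corrected before results are interpreted.

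How often the problem would show depends on two things the documents leave open: the sample size (24 or 12) and the gain from therapy and retesting. Across assumed gains of 0.25 to 1.0 SD and no tDCS effect, Aim 1 is significant in 21% to 99.5% of trials with 24 participants and 11% to 85% with 12.

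**What to change.** Three wording changes:

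1. Reword the Aim 1 heading in both places: *To evaluate the change in picture naming after aphasia therapy preceded by anodal tDCS in people with aphasia after stroke.*
2. Keep the Wilcoxon test and label it: *This tests the combined package (therapy, tDCS and any retest effect).*
3. Add: *Aim 1 does not by itself support a conclusion about tDCS. That conclusion rests on the Aim 2 stimulation-by-time interaction (anodal change minus sham change) for trained and untrained items.*

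Aim 2 does not say whether trained items, untrained items, either or both must show the interaction. The third sentence inherits that gap, so it would be sensible to state the rule at the same time.

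The cost is one heading changed in two places and two added sentences, with no new data, visits or tests. The downside is that Aim 1 can no longer be presented as stand-alone evidence that tDCS works.
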